6.2 Procedures for recording and reporting adverse events (AE)

At the beginning and end of radiotherapy and every follow-up visit, a case report form (CRF) will be filled out by the radiation oncologist, scoring symptoms/adverse events using CTCAEv5.0²⁰ for headache, nausea, epilepsy, gait impairment, dysphasia, dry eye, eye pain, tinnitus, vertigo, vestibular disorder, hearing impaired, vomiting, fatigue, dermatitis, pruritus, scalp pain and cranial nerve impairment.

7. Statistics

7.1 Sample size

Study subjects will be recruited from the radiation-oncology center of three centers: UZ Leuven, UZ Gent and Iridium Kankernetwerk Antwerpen. From a pragmatic perspective, we estimate to recruit 12-15 patients yearly in each of the three centers, resulting in 120 patients in three years in total.

Cognitive impairment has been reported in primary brain tumour patients and is roughly estimated to be present in about half of patients³⁹⁻⁴⁰. Although limited (good quality) evidence exists for our

type of study, power calculations were performed based on the two most extreme studies (i.e. one showing minimal amount of cognitive impairment⁴¹ and one showing maximal amount of cognitive impairment⁴². In both studies cognitive performance is assessed at baseline and about 12 months after radiotherapy in primary brain tumours. In the study by Moretti et al⁴², we used the cognitive outcome results of patients 9-12 months after radiotherapy (45-60 Gy), since the studied population will receive radiotherapy doses within this range. For power calculations, we used the performance on the digit span forward (processing speed) since the prevalence of impairment on this test was low (<20%). Based on these studies, effect sizes of d= 0,368 and d= 1,271 were found with a power of 0,800 and 0,868 respectively. This power would be 0,979 and 1,000 in our specific explorative study, in case of 120 inclusions. In order to detect this difference after 12 months with a power of 0.800 and a two-sided significance level α =0,05, the total required sample size would thus range between 8-60 patients. Power calculations were performed using Gpower 3.1⁴³.

Sample size calculation for the prediction models was performed using a recently developed software package⁴⁴. Since the event rate of cognitive impairment is unclear, we performed power calculations for the lowest and highest event rate, i.e. 0,2-0,5 (see above). When considering 4 candidate predictors and rMSPE of 0,1, the required sample sizes ranges between 90 and 120 patients respectively. Therefore, including 120 patients will allow building a sufficiently complex prediction model combining four dosimetric and/or clinical features.

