4.3 Expected duration of trial

Each participant will be followed at least for two years after radiotherapy. The trial will be regarded as completed when 120 patients will have reached a follow-up of two years. Since neurocognitive decline is considered to be progressive, participants will still be in follow-up after completion of the trial according to the clinical practice guidelines.

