4.4 Subject discontinuation or withdrawal

Participation can be discontinued at any time if the subject, the Investigator, or the Sponsor feels that it is not in the subject's best interest to continue. The following is a list of possible reasons for study treatment discontinuation:

- Screening failure
- Subject withdrawal of consent
- Subject is not compliant with study procedures
- Lost to follow-up
- Sponsor request for early termination of study
- Subject death
- Progressive disease or relapse during follow-up

All subjects are free to withdraw from participation at any time, for any reason, specified or unspecified, and without prejudice. Reasonable attempts will be made by the Investigator to provide a reason for subject withdrawals. The reason for the subject's withdrawal from the study will be specified in the subject's source documents and the Case Report Form (CRF). The Investigator will make every effort to contact subjects who are lost to follow-up. Attempts to contact such subjects must be documented in the subject's records (e.g., times and dates of attempted telephone contact, receipt for sending a registered letter, etc.). Subjects who prematurely discontinue are not to be replaced. For subjects considered lost to follow-up, the CRF must be completed up to the last visit performed.

5. Trial Procedures

Subjects will be screened at the consultation of the neurosurgeon (after biopsy or surgery) or after physician referral to the local radiotherapy-oncology centre. This study will be listed at www.clinicaltrials.gov.

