7.2.1 Neuropsychological data

The following research questions are addressed by using multiple statistical tests.

- 1. How severe is the neurocognitive decline after treatment and how does it change over time?
- 2. Which neurocognitive domains are affected in which patients?

The first question is addressed by investigating the neurocognitive performance of primary brain and base of skull tumour patients. The performance on neurocognitive measures of the patients will be assessed at 3 timepoints over time. The raw test-scores are converted to normalized zscores based on normative data for each cognitive test. For each cognitive test, cognitive impairment is defined as a z-score \leq 1.5, and patients will be dichotomized according to their impairment status (impaired versus unimpaired). The frequency of impairment will be reported as descriptive information.

We will assess the evolution in the z-scores with a mixed repeated measures model to test changes throughout time. However, if the data are not normally distributed, the Friedman test will be used as alternative approach. The effects of the patient- and treatment-related predictors on the neuropsychological and questionnaire scores will be investigated using general linear models (predictors= tumour location, radiation dose, covariates= gender, age at treatment, time since treatment and socio-economic status) at each timepoint. Bonferroni correction will be applied as

method for statistical correction of multiple tests, for each test outcome (n=5 outcomes; memory, executive functioning, attention, visuomotor function, working memory) that is predicted.

Effect sizes of the tests will be reported. Partial eta squared (hp2) will be computed to estimate effect sizes (weak effect: $np^2 \approx 0.03$; moderate: $np^2 \approx 0.06$; large: $np^2 \geq 0.14$) for linear relationships between predictor and each outcome (e.g. age, time since treatment). Cohen's d will be used to estimate effect sizes for subgroup differences (small effect: 0.2 < d < 0.3; medium: 0.3 < d < 0.8; large: d > 0.8).

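### Section 7.1 bases power and model size on 120 inclusions with no allowance for loss, and the completion rule in section 4.3 cannot be met once one patient is lost

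*Protocol*

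**What the plan says.** Section 7.1 of the protocol sizes the study in two ways.

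The first concerns the change from baseline to about 12 months on a single test, digit span forward. Two published studies supply the inputs: "effect sizes of d= 0,368 and d= 1,271 were found with a power of 0,800 and 0,868 respectively". The section continues: "This power would be 0,979 and 1,000 in our specific explorative study, in case of 120 inclusions". It adds that, "with a power of 0.800 and a two-sided significance level α =0,05", "the total required sample size would thus range between 8-60 patients".

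The second concerns the prediction model. With four candidate predictors and an rMSPE of 0.1, the need is put at 90 patients for event rate 0.2 and 120 for event rate 0.5. Enrolment is 120, and the section concludes that this supports a four-feature model. Neither calculation mentions patients who never reach the one-year test.

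Section 4.4 names death, loss to follow-up, withdrawal of consent and "Progressive disease or relapse during follow-up" among the possible reasons for leaving, and states: "Subjects who prematurely discontinue are not to be replaced". A footnote to the visit table in section 5.1 places the end-of-study visit at two years or at progression. Section 4.3 says: "The trial will be regarded as completed when 120 patients will have reached a follow-up of two years".

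Section 7.2.1 describes a mixed model for change over time, then general linear models for the predictors. It then applies a Bonferroni correction "for each test outcome (n=5 outcomes; memory, executive functioning, attention, visuomotor function, working memory) that is predicted". Section 7.2.3 tests at an uncorrected 0.05.

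**The concern.** Both calculations count patients who enter the study, but both analyses need patients with a one-year cognitive result. The protocol itself foresees that these numbers will differ, since patients can die, be lost or progress, and none is replaced. The stated power is therefore an upper limit. For the NTCP model, which is the primary objective, the upper requirement equals the enrolment target, so nothing is left for losses.

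The same gap makes the end-of-trial definition unreachable. With 120 enrolled and no replacement, 120 patients can reach two years only if nobody is lost.

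A smaller issue is the significance level. The power calculation uses 0.05 on one test, while the analysis section announces a correction over five outcomes without saying whether it covers the test that was powered.

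**Working it through.** **Inputs.** From section 7.1: d = 0.368 and d = 1.271, two-sided alpha 0.05, target power 0.80, 120 inclusions, and a model need of 90 (event rate 0.2) to 120 (event rate 0.5). From section 7.2.1: five outcomes, so a Bonferroni level of 0.05/5 = 0.01. This level is derived; the protocol does not print it. The protocol gives no loss rate, so 10 to 30% is my assumed range.

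**Method.** Paired t-test with n evaluable patients. The test statistic follows a noncentral t distribution with n − 1 degrees of freedom and noncentrality d × √n. Power is the probability that it falls beyond the two-sided critical value.

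**Step 1: the plan's own figures, alpha 0.05.**
- d = 0.368, n = 60: noncentrality 0.368 × √60 = 2.85, power 0.801. The smallest n for 0.80 is 60, as stated.
- d = 0.368, n = 120: noncentrality 0.368 × √120 = 4.03, power 0.979, as stated.
- d = 1.271, n = 8: noncentrality 1.271 × √8 = 3.59, power 0.867 against 0.868 stated. The smallest n for 0.80 is 8, as stated.
- d = 1.271, n = 120: noncentrality 13.92, power 1.000, as stated.

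The arithmetic is sound. A one-sided test (0.991 at 120) and a two-sample comparison of 60 with 60 (0.522) do not give 0.979, so the paired two-sided reading is the right one.

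**Step 2: the same test after loss, d = 0.368.**

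| Loss before one year | Evaluable of 120 | Power, alpha 0.05 | Power, alpha 0.01 |
|---|---|---|---|
| 0% | 120 | 0.979 | 0.919 |
| 10% | 108 | 0.966 | 0.883 |
| 20% | 96 | 0.946 | 0.833 |
| 25% | 90 | 0.932 | 0.802 |
| 30% | 84 | 0.915 | 0.767 |

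**Step 3: required n at alpha 0.01.** For power 0.80 it is 90 for d = 0.368 and 11 for d = 1.271, so 8–60 would become 11–90. At alpha 0.01, 60 patients give power 0.577.

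**Step 4: the model.** At event rate 0.5 the margin is 120 − 120 = 0 patients. At event rate 0.2 it is 120 − 90 = 30 patients, and 30/120 = 25%.

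**Step 5: the completion rule.** If L patients are lost before two years and none is replaced, 120 − L reach two years. The rule in section 4.3 requires 120 − L = 120, hence L = 0.

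**The case against.** The best defence is that the change test is comfortably powered. At the plan's own alpha of 0.05, power is still 0.915 after 30% loss. Even at 0.01 it stays above 0.80 until about 25% are lost. The 0.979 is worded conditionally, the study is described as exploratory, and the powered comparison falls at one year, so not every loss over two years counts against it. Section 4.4 also gives only possible reasons for leaving, so progression need not end participation in every case. All of this stands, and it limits the power issue to a correction of stated figures. It does not help the model at event rate 0.5 or the completion rule, because death and loss to follow-up are exits in any case and the section 5.1 footnote foresees exit at progression.

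Three stronger readings are tempting, but the document does not support them.

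- A reader might infer that the powered test is run at 0.01. The Bonferroni sentence follows the predictor models and is limited to outcomes being predicted, no correction is attached to the mixed model for change, and section 7.2.3 uses 0.05. The scope is unclear; a contradiction is not shown.
- A reader might infer that every figure in section 7.1 rests on alpha 0.05 and 120 evaluable patients. The 8–60 range is a required number and does not presume 120 patients. The model size rests on rMSPE and event rate and uses no alpha.
- A reader might want the model's loss of precision, or the number of predictors it could still support, as a figure. That needs the formula of the cited package, which the protocol does not give, so no such figure is offered here.

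**Conclusion.** The point holds for the absence of any loss allowance and for the completion rule. Sections 4.3 and 4.4 and the sample size of 120 are compatible only with zero loss over two years, which follows without any assumption. The model requirement at event rate 0.5 has no margin, so the conclusion in section 7.1 that 120 inclusions suffice for four features is not assured at that rate. At event rate 0.2 it survives up to 25% loss.

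The power figure of 0.979 is correctly computed but is a best case. Under the assumed 10 to 30% loss it becomes 0.966 to 0.915 at alpha 0.05, and 0.883 to 0.767 if the Bonferroni correction applies. The document does not support calling 120 too small for the change test: power falls below 0.80 only if alpha 0.01 and more than about 25% loss both apply. The loss range is an assumption, and the alpha 0.01 column depends on a scope that the protocol leaves open.

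**What to change.** - **Section 4.3:** define the trial as complete when every enrolled patient has reached two years after radiotherapy or has discontinued. This removes the conflict with section 4.4.
- **Section 7.1, power:** state an expected loss before the one-year test and give power on evaluable patients. For d = 0.368 at alpha 0.05 this is 0.966, 0.946 and 0.915 at 10, 20 and 30% loss.
- **Section 7.2.1:** say which tests the Bonferroni correction covers. If it covers the change-over-time test, restate the required number in section 7.1 as 11–90 and the power as 0.919 at 120 evaluable patients (0.883, 0.833 and 0.767 at 10, 20 and 30% loss).
- **Section 7.1, model:** say that at event rate 0.5 the four-predictor model meets an rMSPE of 0.1 only with 120 evaluable patients, and set the maximum number of predictors from the evaluable number with the cited package.

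The cost is protocol wording, and the stated figures become less favourable. Extra recruitment is not needed for the change test unless alpha 0.01 and more than about 25% loss both apply. If the sponsor prefers to keep 120 evaluable patients for the model, enrolment of 120/(1 − loss) would be 134, 150 or 172 at 10, 20 or 30% loss. The accrual estimate in section 7.1 implies 3 centres × 12–15 per year × 3 years = 108–135, so anything beyond 10% would probably lengthen recruitment.

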3.2 Primary endpoints

- Predict neurocognitive decline based on RT dosimetric and other explanatory variables like gender, age at diagnosis, comorbidities, level of education, social factors such as social activity and occupation, tumour size and localization, pathological/genetic/molecular characteristics, therapy protocols (surgery, radiotherapy and/or chemotherapy) in an NTCP model for each cognitive domain
- Measure the prevalence and severity of neurocognitive decline compared to baseline at one year, for all cognitive domains (attention, memory, working memory, information/visuomotor processing speed, executive functioning)

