7.2.4 NTCP modeling

Two NTCP modelling efforts will be conducted for each cognitive outcome domain (attention, memory, executive functioning, working memory, Information/visuomotor processing speed). In the first effort, dose metrics of anatomical structures derived from a brain atlas will be used together with clinical patient factors to develop a prediction model of neurocognitive decline. First, univariable logistic regression analysis will be performed to select clinical parameters associated with cognitive outcome. These variables will be ranked based on their association (area under the curve (AUC) of the univariable logistic regression) with the endpoint. The best ranked variable will be selected first. Subsequently, each next variable will be excluded from the ranking if its Pearson's correlation is r > 0.8 with any previously selected variable. For the remaining variables, we will check whether non-linear transformations (log, square root, inverse transformations, etc.) improves the association. Considered clinical variables in model building are: gender, age at diagnosis, tumour location, treatment modality, pathology, education, time since treatment. The added value of dosimetry to the use of clinical information will be verified in three steps. Initially,

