a multivariable prediction model (logistic regression model with LASSO regularization) will be built with only the clinical variables using a forward stepwise procedure with p = 0.05 (deviance criterion) as critical p-value to stay in the model. Afterwards, the clinical prediction model will be extended by a stepwise addition of dosimetric variables which are ranked in the univariable analysis. In this multivariable prediction model (LASSO), a maximum of 4 variables will be included in each model. Finally, we will test in all models whether proton beam therapy (PBT) itself has an additional independent impact on the outcome risk apart from the already selected dose metrics. If that is the case, this will be investigated further by linear energy transfer (LET) and relative biological effectiveness (RBE) weighted PBT dose maps instead of the standard (RBE=1.1) PBT dose maps. The discriminative ability of the prediction models will be quantified using the AUC and compared between nested models using the likelihood ratio test. To obtain stable prediction models, all modelling steps will be repeated in a 100 times repeated 5-fold cross-validation process. The most frequently obtained models will be selected. Final model coefficients will be determined by fitting these selected models on the complete development dataset. Correction for optimism will be performed using 500 bootstrap samples.

In a second effort, relevant 3D clusters of brain voxels resulting from the brain damage susceptibility heat maps will be included in the modelling. Dose to these brain areas will be used as alternative dosimetric input parameters and the resulting model's performance will be compared to that obtained in the first step. The final NTCP model parameters will be calculated for the whole dataset of patients and per institution in order to detect potential heterogeneity.

Internal validation of the model will be performed using bootstrapping. After external validation, the final NTCP models could possibly be included in decision support software. In case of conflicting neurotoxicity constraints, several 'optimal' solutions to the planning problem (prioritizing one or another brain region) might indeed be possible. This will facilitate plan comparisons and informed decisions on the optimal treatment plan in future patients.

8. Quality assurance

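### The prediction-model sample size assumes four candidate predictors, but section 7.2.4 uses four only as the ceiling on a model chosen from a larger search, so the rMSPE of 0.1 is not secured at n=120

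*Protocol*

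**What the plan says.** Section 7.1 takes two event rates: "we performed power calculations for the lowest and highest event rate, i.e. 0,2-0,5 (see above". For these it states: "When considering 4 candidate predictors and rMSPE of 0,1, the required sample sizes ranges between 90 and 120 patients respectively". It then concludes that "including 120 patients will allow building a sufficiently complex prediction model combining four dosimetric and/or clinical features".

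Section 7.2.4 describes how the models will be built. The clinical list reads: "Considered clinical variables in model building are: gender, age at diagnosis, tumour location, treatment modality, pathology, education, time since treatment". These variables are screened by univariable logistic regression, ranked by AUC and filtered for high correlation. For those that remain, "we will check whether non-linear transformations (log, square root, inverse transformations, etc.) improves the association". A forward stepwise LASSO logistic model at p = 0.05 follows. Atlas dose metrics, also ranked univariably, are then added stepwise. The number four appears here in another role: "a maximum of 4 variables will be included in each model". A proton-therapy term is tested afterwards. A second, separate effort replaces the atlas dose metrics with doses to voxel clusters.

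Section 3.2 describes the explanatory variables more widely still: "explanatory variables like gender, age at diagnosis, comorbidities, level of education, social factors such as social activity and occupation, tumour size and localization", among others.

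**The concern.** Sections 7.1 and 7.2.4 use the same number for two different quantities. In 7.1 it is the count of predictors considered; in 7.2.4 it is the most that may remain after selection. The two agree only if nothing is selected using the outcome. Here selection does use the outcome, and each choice among competing variables or transformations adds error to the predicted risks that a four-predictor calculation leaves out.

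The rMSPE is the root mean squared difference between predicted and true risk in new patients. It is the right quantity to worry about, because section 3.1 intends the models to support the choice of treatment modality for individual patients. This calculation is also the sample-size justification for the primary objective. If its input is wrong, a reader of 7.1 will credit the individual risks with a precision that the planned procedure does not reach.

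**Working it through.** **Inputs.** From 7.1: P = 4 candidates, target rMSPE 0.1, event rate φ = 0.2 or 0.5, n = 120, stated requirement 90 and 120. From 7.2.4: seven named clinical candidates, dose metrics of unstated number, forward p = 0.05, LASSO, ceiling of four. Assumed, because the protocol gives none: predictor effects (four true predictors, log-odds 0.3 to 0.5 per SD, correlation 0.3 in the selection runs) and candidate totals of 15 and 30 once dose metrics are included.

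**Step 1: reproduce the plan's figure.** A first-order approximation is n = φ(1−φ)(P+1)/rMSPE².

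- φ = 0.2: 0.16 × 5 / 0.01 = 80
- φ = 0.5: 0.25 × 5 / 0.01 = 125

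This is the right order but not exact. Simulating a maximum-likelihood logistic model with four independent predictors fixed in advance (log-odds 0.3), and solving for rMSPE = 0.1, gives 91 and 123 against the stated 90 and 120. The arithmetic in 7.1 is therefore sound for four predictors in total and no selection.

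**Step 2: count the candidates.** The clinical list alone has seven entries. Tumour location, treatment modality and pathology may each need more than one parameter, so seven is a low count. Dose metrics come on top. Three things are left out of the count: the transformations (they suit only continuous variables that survive the correlation filter), the voxel clusters (alternative inputs in a separate effort) and the proton term (tested after selection).

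**Step 3: correct the input, keep the method of 7.1.** With P = 7 the approximation gives 0.16 × 8 / 0.01 = 128 and 0.25 × 8 / 0.01 = 200. The simulation gives about 148 and 193. All four exceed 120. This step assumes all seven are fitted without penalty, which is not the plan, so step 4 is the relevant one.

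**Step 4: rMSPE at n = 120 under procedures close to the plan** (φ = 0.2 / φ = 0.5).

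| Procedure | 7 candidates | 15 (assumed) | 30 (assumed) |
|---|---|---|---|
| Forward, p < 0.05, at most 4 | 0.115-0.129 / 0.138-0.140 | 0.135-0.147 / 0.157-0.163 | 0.158-0.167 / 0.175-0.184 |
| LASSO, cross-validated penalty | 0.094-0.095 / 0.112 | 0.101-0.112 / 0.125-0.129 | 0.102-0.125 / 0.132-0.138 |

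For comparison, four predictors fixed in advance in the same setting give 0.085-0.086 / 0.090-0.091. A separate simulation of the forward procedure gave 0.116 / 0.140 with seven candidates and 0.13 / 0.16 with 15. Section 7.2.4 combines stepwise selection with LASSO, so both rows are shown. The LASSO row imposes no ceiling of four and rests on 60 simulated data sets per cell, so its third decimal should not be pressed; 0.101 and 0.102 lie at the target within that error.

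**Step 5: read the table.** With seven candidates and the ceiling of four, the forward rMSPE is clearly above that of four fixed predictors at both event rates. LASSO clears 0.1 only with seven clinical candidates at event rate 0.2, and a model without dose metrics is not the NTCP model the trial is for. If no candidate had any effect, forward selection from seven would also stay below 0.1 (0.072 / 0.083), but such a model would predict nothing.

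**The case against.** Three counter-arguments deserve weight.

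First, the plan includes protection: LASSO shrinkage, repeated cross-validation, a small final model and bootstrap optimism correction. This stands in part. Shrinkage recovers much of the loss, and at the lower event rate with weak effects LASSO is near the target even with 15 or 30 candidates. Optimism correction, however, reports overfitting; it does not make the predicted risks more precise.

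Second, the number of dose metrics is not given and may be fixed elsewhere. This also stands, and it is why 15 and 30 are labelled as assumptions. It does not remove the mismatch, since the seven clinical variables in the protocol already exceed four.

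Third, the study calls itself exploratory, sets recruitment pragmatically and foresees external validation before any decision-support use. That lowers the immediate consequence, as no patient's treatment in this study depends on the model. It does not excuse a stated precision target that rests on the wrong input.

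A reader might go further and infer an rMSPE of roughly 0.17 to 0.23, or a need for 336 to 525 patients. Those figures come from an unpenalised fit of 15 to 20 candidates at once (the patient numbers from 20), which section 7.2.4 does not plan, and the counts are not in the protocol. A reader might also infer that the model would do no better than giving everyone the average risk. With an AUC of about 0.70 and 12 assumed candidates, LASSO at n=120 gave 0.111 against 0.122 for the average risk (event rate 0.2) and 0.139 against 0.177 (0.5). The gain is modest at the lower rate, but it is there.

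**Conclusion.** The mismatch is real: a wrong input to a correct calculation, not an arithmetic error. At n=120, the planned kind of search from seven to 15 candidates gives an rMSPE of about 0.095 to 0.15 at event rate 0.2 and 0.11 to 0.16 at event rate 0.5, depending on whether LASSO or forward selection dominates. The target of 0.1 is met only at the favourable end. The direction is firm for forward selection whenever real effects exist. The size depends on the assumed effects, the assumed correlation and the number of dose metrics, so it should be quoted as a range. The documents do not support saying that the target is missed in every case, or that voxel clusters add to the count of the first modelling effort.

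**What to change.** Choose one of two changes.

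(a) Keep the search. In 7.1, state the number of candidate parameters per domain (clinical variables counted by category, plus the dose metrics), give the rMSPE expected at n=120 from a simulation of the actual stepwise/LASSO procedure at both event rates, and withdraw the claim that 0.1 is met. The figure should come from the planned procedure and not from an unpenalised fit of all candidates.

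(b) Keep the precision claim. Name at most four candidate parameters per cognitive domain without looking at the outcome, counting each category of a multi-level variable. Fit them by penalised logistic regression with no univariable screening and no transformation search. Retain the wider atlas and voxel-cluster work, labelled exploratory.

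Either is a change of wording with no effect on recruitment or data collection. The cost of (a) is a less favourable stated precision; the cost of (b) is fewer brain structures in the primary model.

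### The single absolute-error target (rMSPE 0.1) behind the model sample size does not by itself show that 120 patients support four features in low-event cognitive domains

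*Protocol*

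**What the plan says.** Protocol section 7.1 treats the event rate as uncertain: "we performed power calculations for the lowest and highest event rate, i.e. 0,2-0,5 (see above"). With four candidate predictors it then reports: "When considering 4 candidate predictors and rMSPE of 0,1, the required sample sizes ranges between 90 and 120 patients respectively". So 90 belongs to event rate 0.2 and 120 to event rate 0.5. The method is a cited software package, and no formula is shown. The section concludes that "including 120 patients will allow building a sufficiently complex prediction model combining four dosimetric and/or clinical features". It gives no expected AUC, R-squared, spread of true risks or shrinkage target, and no comparison with a model without predictors. Earlier, the same section reports a prevalence of impairment under 20% for one test, digit span forward.

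Section 7.2.4 builds a model for each of five cognitive domains. It specifies that "a maximum of 4 variables will be included in each model", without linking that cap to the number of events. Discrimination is measured by AUC, and nested models are compared by likelihood ratio test. It adds that "Correction for optimism will be performed using 500 bootstrap samples", but does not say which measures are corrected. Calibration is not named.

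**The concern.** Read as written, 7.1 presents the low event rate as the less demanding case, needing 90 patients against 120. For the stability of a model the reverse is true, because fewer events leave less information per coefficient. The low-rate figure is smaller only because the target is in absolute percentage points and, when the average risk is low, the variance of an estimated risk is small whether or not the predictors carry information.

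Section 3.1 intends these models to help choose the treatment modality for individual patients. For that use, individual risks must be well calibrated and better than quoting the average. A domain with few events could pass the sizing criterion and still fail on both counts, and the measures named in 7.2.4 would not necessarily show it.

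**Working it through.** **Inputs from the protocol.** P = 4 predictors; rMSPE target 0.1; event rates 0.2 and 0.5 (all 7.1); planned N = 120. The protocol gives no predictive strength, so the AUC values below are assumptions shown as a range.

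**1. Reproduce 90 and 120.** A large-sample approximation is rMSPE² = φ(1−φ)(P+1)/N, so N = φ(1−φ)(P+1)/0.01.
- φ = 0.2: 0.16 × 5 / 0.01 = 80.
- φ = 0.5: 0.25 × 5 / 0.01 = 125.

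Simulation is closer: four independent normal predictors of equal strength, unpenalised logistic regression, solving for the N at which the root of the mean squared prediction error is 0.1. At rate 0.2 it gives N of 89 to 91 for AUCs from about 0.58 to 0.74. At rate 0.5 it gives 125 down to 108 over the same range, and 118 at AUC of about 0.66. The stated figures are therefore sound. The 90 hardly moves with AUC, so reaching it says nothing about whether the predictors are informative.

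**2. Direction of the criterion.** Required N in the approximation is proportional to φ(1−φ), so it falls as events get rarer. In events, the protocol's own figures imply 90 × 0.2 = 18 at the low rate and 120 × 0.5 = 60 at the high rate, for the same four coefficients. At an illustrative rate of 0.1 the approximation asks for 0.09 × 5 / 0.01 = 45 patients, or 4.5 events.

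**3. What a constant prediction scores.** If everyone is given 20% and the true mean is 20%, the rMSPE equals the standard deviation (SD) of the true risks. The constant meets the target when SD ≤ 0.10. For a normal linear predictor with mean risk 0.2 that corresponds to an AUC of up to about 0.67. If the rate is itself estimated from 120 patients, the limit is √(0.01 − 0.16/120) = 0.093, or AUC about 0.66. At event rate 0.5 a constant 50% meets 0.1 only up to AUC about 0.61.

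**4. The planned size at the low rate (N = 120, φ = 0.2, so 24 expected events).** The last three columns come from the simulated model. The fourth compares it with the average rate observed in the same data.

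| Assumed AUC | rMSPE of constant 20% | rMSPE of model | Model worse than observed average rate | Median calibration slope |
|---|---|---|---|---|
| 0.60 | 0.058 | about 0.086 | about 73% | about 0.38 |
| 0.65 | 0.086 | about 0.086 | about 31% | about 0.60 |
| 0.70 | 0.119 | about 0.086 | about 7% | about 0.73 |

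Repeat runs put the fourth column at 66% to 73%, 26% to 31%, and below 10%. The criterion is passed in every row. A slope of 1 is ideal; 0.60 means the predicted log-odds are spread much too widely.

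**5. Below the stated floor (illustrative rate 0.1, N = 120, so 12 events).** The model's rMSPE is 0.071 to 0.073, an easier pass. Median slopes are 0.26 to 0.57 over AUC 0.60 to 0.70, and the model does worse than the average rate in about 85%, 61% and 38% of datasets.

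**The case against.** The case for leaving 7.1 alone has weight, and several stronger readings do not hold.

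- A reader might infer that the sample size was miscalculated. It was not. Needing fewer patients at a low rate is how any absolute-error target behaves.
- A reader might infer that a constant 20% always meets the target. It does so only up to AUC of about 0.67. At 0.70 the constant scores about 0.12 and fails, while the model passes. The protocol gives nothing that places the trial on either side.
- A reader might attack the 90. The plan relies on 120. There, at rate 0.2 and AUC 0.65, the model's average error (about 0.086) is already slightly below that of a rate estimated from the data (0.095 in one check).
- A reader might take the prevalence under 20% as proof that a domain falls below 0.2. It describes one test, and most domains combine several, so it only suggests that some outcomes may lie lower.
- The slopes come from an unpenalised fit, whereas 7.2.4 plans LASSO, cross-validation and bootstrap correction, and its cap of four allows fewer. Penalisation should improve the slopes. However, 7.2.4 also uses stepwise selection at p = 0.05 and fits the selected models again on the full dataset, and 7.1 claims no benefit from shrinkage.
- The study calls itself exploratory and plans later validation. That limits the harm but does not supply the missing support for the claim in 7.1.

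What remains is that passing the one stated criterion is compatible with a model no better than the average risk.

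**Conclusion.** The concern holds in a limited form. The figures in 7.1 are right, but at event rate 0.2 they do not by themselves establish that 120 patients support four features. Whether they do depends on a predictive strength that the protocol never states. If the true AUC is about 0.70, the model usually beats the average rate but still has a median slope of only about 0.73. If it is about 0.60, the model loses to the average in roughly two thirds to three quarters of datasets.

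These results assume four predictors fixed in advance, independent and normal, unpenalised fitting and complete outcomes. Fixing the predictors is lenient to the plan, since 7.2.4 screens seven clinical variables and then dosimetric ones; that is a separate matter. The unpenalised fit is severe on it.

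It would go too far to conclude that 120 patients are too few or that recruitment must rise. No event-rate threshold for safe four-feature models follows either: at rate 0.5 and AUC about 0.70 the median slope at N = 120 is still only about 0.79.

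**What to change.** In 7.1, make the four-feature claim conditional on an assumed AUC or R-squared and on the number of events. Beside rMSPE, give the expected calibration slope at N = 120 for a set of event rates that includes values below 0.2. Do not present the low event rate as the less demanding case.

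In 7.2.4, report for each domain model, beside AUC, the optimism-corrected calibration slope and the Brier score against the average-risk prediction. Do not put forward as an NTCP model any model that fails to beat the average risk.

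The cost is a reworded paragraph and slightly more analysis, using the bootstrap already planned. No extra patients are needed and no event-rate cut-off has to be set. The downside is that the stated justification becomes less favourable for low-event domains, and some domains may end without a usable model.
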